12.5 Management Algorithms for Immuno-Oncology Agents

Immuno-oncology (I-O) agents are associated with AEs that can differ in severity and duration than AEs caused by other therapeutic classes. Nivolumab is considered immuno-oncology agents in this protocol. Early recognition and management of AEs associated with immuno-oncology agents may mitigate severe toxicity. Management Algorithms have been developed to assist investigators in assessing and managing the following groups of AEs:

- Gastrointestinal

- Renal
- Pulmonary
- Hepatic
- Endocrinopathy
- Skin
- Neurological

The above algorithms are found in Appendix II.

12.6 Treatment of infusion reactions

Since nivolumab contains only human immunoglobulin protein sequences, it is unlikely to be immunogenic and induce infusion or hypersensitivity reactions. However, if such a reaction was to occur, it might manifest with fever, chills, rigors, headache, rash, pruritus, arthralgias, hypo- or hypertension, bronchospasm, or other symptoms. All Grade 3 or 4 infusion reactions should be reported within 24 hours to IFCT and reported as an SAE if criteria are met. Infusion reactions should be graded according to NCI CTCAE (Version 4.0) guidelines.

Treatment recommendations are provided below and may be modified based on local treatment standards and guidelines, as appropriate:

For Grade 1 symptoms (mild reaction; infusion interruption not indicated; intervention not indicated):

- Remain at bedside and monitor subject until recovery from symptoms. The following prophylactic premedications are recommended for future infusions: diphenhydramine 50 mg (or equivalent) and/or acetaminophen/paracetamol 325 to 1000 mg at least 30 minutes before additional nivolumab administrations.

For Grade 2 symptoms: (moderate reaction requires therapy or infusion interruption but responds promptly to symptomatic treatment (antihistamines, non-steroidal anti-inflammatory drugs, narcotics, corticosteroids, bronchodilators, IV fluids); prophylactic medications indicated for \leq 24 hours).

- Stop the nivolumab infusion, begin an IV infusion of normal saline, and treat the subject with diphenhydramine 50 mg IV (or equivalent) and/or acetaminophen/paracetamol 325 to 1000 mg; remain at bedside and monitor subject until resolution of symptoms. Corticosteroid and/or bronchodilator therapy may also be administered as appropriate. If the infusion is interrupted, then restart

the infusion at 50% of the original infusion rate when symptoms resolve; if no further complications ensue after 30 minutes, the rate may be increased to 100% of the original infusion rate. Monitor subject closely. If symptoms recur, then no further nivolumab will be administered at that visit. Administer diphenhydramine 50 mg IV, and remain at bedside and monitor the subject until resolution of symptoms. The amount of study drug infused must be recorded on the electronic case report form (eCRF).

- For future infusions, the following prophylactic premedications are recommended: diphenhydramine 50 mg (or equivalent) and/or acetaminophen/paracetamol 325 to 1000 mg should be administered at least 30 minutes before nivolumab infusions. If necessary, corticosteroids (up to 25 mg of SoluCortef or equivalent) may be used.

For Grade 3 or 4 symptoms: (severe reaction, Grade 3: prolonged [i.e., not rapidly responsive to symptomatic medication and/or brief interruption of infusion]; recurrence of symptoms following initial improvement; hospitalization indicated for other clinical sequelae [e.g., renal impairment, pulmonary infiltrates]. Grade 4: Life threatening; pressor or ventilatory support indicated)

- Immediately discontinue infusion of nivolumab. Begin an IV infusion of normal saline and treat the subject as follows: Recommend bronchodilators, epinephrine 0.2 to 1 mg of a 1:1000 solution for subcutaneous administration or 0.1 to 0.25 mg of a 1:10,000 solution injected slowly for IV administration, and/or diphenhydramine 50 mg IV with methylprednisolone 100 mg IV (or equivalent), as needed. Subject should be monitored until the investigator is comfortable that the symptoms will not recur. Nivolumab will be permanently discontinued. Investigators should follow their institutional guidelines for the treatment of anaphylaxis. Remain at bedside and monitor subject until recovery of the symptoms.

In case of late-occurring hypersensitivity symptoms (e.g., appearance of a localized or generalized pruritus within 1 week after treatment), symptomatic treatment may be given (eg, oral antihistamine or corticosteroids).

13 DATA ANALYSIS AND STATISTICAL CONSIDERATIONS

13.1 Study design considerations

The maximum sample size (N) is calculated based on α , β , and the expected effect size, using a test for single binomial proportion for a two-stage design with O'Brien-Fleming (OF)

stopping rules, allowing for early stopping for futility after Stage I. The software East 6.0 was used

13.2 Sample size assumption

It is a phase II non randomized, multicenter, open study, assessing nivolumab efficacy.

Tested hypothesis

The hypothesis underscoring our study is that the disease is controlled (stable disease or response) in at least 57% of patients at first evaluation (8 weeks) of nivolumab therapy.

H_0 : control rate $\leq 30\%$ (unacceptable control rate)

H_1 : control rate $\geq 57\%$ (acceptable control rate)

$\alpha=5\%$ (one-sided), $\beta=90\%$

Step 1 (n=14 patients): ≤ 4 patients with a disease controlled \rightarrow futility (H_0 accepted)

Final decision (n=28 patients): ≥ 13 patients with a disease controlled \rightarrow rejected H_0 (positive trial)

30 patients included, taking into account possible non eligible patients (5%)

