3 REGIMEN

Thirty eligible patients, previously treated by at least one line of platinum-based chemotherapy, will be included.

[figure not shown]
TREATMENT:

Nivolumab is administered intravenously (IV), over 30 minutes at 3 mg/kg every 2 weeks, until disease progression, death, limiting toxicity or patient refusal.

Premedication is not required.

Patients with tumoral progression will stop the treatment but will have a follow-up for the secondary endpoints of OS, and the toxicities assessment till a last study visit 4 weeks (\pm 1 week) after the last injection of the drug.

Twenty centers will be opened.

Schedule of the study design.

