13.4 Efficacy Analyses

13.4.1 Primary endpoint analysis

Analysis of the primary efficacy endpoint will be conducted on all eligible patients, based on the disease control rate after 8 weeks of treatment. Analysis of the primary efficacy endpoint will be also conducted on all patients (ITT analysis) as sensitivity analysis.

It will be presented associated with its 95% confidence interval. Patients for whom the answer cannot be evaluated will be considered as treatment failures.

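### The success rule of 13 controlled is fixed for 28 patients, but the primary analysis takes every eligible patient among 30 and has no cut-off for 29 or 30

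*Protocol*

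**What the plan says.** Protocol section 13.1 describes a two-stage single-proportion design with a futility stop after stage 1. Section 13.2 sets a null control rate of 30%, an alternative of 57% and a one-sided alpha of 5%. Stage 1 has 14 patients, with a stop if 4 or fewer are controlled. The final rule is headed "Final decision (n=28 patients)" and calls the trial positive with 13 or more controlled. The enrolment target follows: "30 patients included, taking into account possible non eligible patients (5" per cent).

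Section 13.4.1 names the primary population: "Analysis of the primary efficacy endpoint will be conducted on all eligible patients". Section 13.3 defines these as intention-to-treat patients without a major deviation on the entry criteria, and puts no limit on their number. Under section 13.4.1, patients who cannot be evaluated count as failures, so they stay in the denominator. The ITT sensitivity analysis uses all included patients.

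Section 3 describes the target differently: "Thirty eligible patients, previously treated by at least one line of platinum-based chemotherapy, will be included".

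**The concern.** The decision rule belongs to one sample size and the primary population to another. Nothing in sections 13.2, 13.3 or 13.4.1 brings the analysed set back to 28, and nothing gives a threshold for any other number. With 29 or 30 eligible patients, a reader who follows 13.2 and 13.4.1 together has only the figure 13 to apply, and 13 is too low there to hold 5%.

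This rule decides whether the trial is positive. With exactly 13 controlled among 29 or 30 eligible patients, the verdict depends on whether 13 is kept, the cut-off is raised to 14, or the set is trimmed to 28. The trial is open-label. Under section 13.3 the principal investigators classify deviations as major or minor, which sets the eligible number, and the section does not say that this happens before outcomes are known.

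**Working it through.** **Inputs (section 13.2).** p0 = 0.30; p1 = 0.57; one-sided alpha 0.05; target power 90% (printed as beta); n1 = 14, stop at 4 or fewer; final n = 28, success at 13 or more; 30 included for 5% ineligible.

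**Formula.** With exactly 14 patients at stage 1, final number n and cut-off c:

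P(success) = sum over x = 5 to 14 of P[Bin(14, p) = x] × P[Bin(n − 14, p) ≥ c − x].

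At p = 0.30 this is the type I error, and at p = 0.57 the power.

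**1. The plan's own design reproduces.** At n = 28, c = 13, type I error is 4.69% and power 89.6%. Ignoring the futility stop, they are 4.91% and 90.6%. A cut-off of 12 would give 9.4%, so 13 is right at 28. The inflation is also right: 28 / 0.95 = 29.5, rounded up to 30.

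**2. Other numbers of eligible patients.**

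| n | cut-off | type I error | power |
|---|---|---|---|
| 26 | 13 | 2.5% | 81.7% |
| 27 | 13 | 3.5% | 86.2% |
| 28 | 13 | 4.7% | 89.6% |
| 29 | 13 | **6.1%** | 92.0% |
| 30 | 13 | **7.7%** | 93.7% |
| 29 | 14 | 2.8% | 86.4% |
| 30 | 14 | 3.8% | 89.6% |

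Without the futility stop, cut-off 13 gives 6.5% at 29 and 8.4% at 30, so the excess does not depend on whether that stop is binding.

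**3. How often this arises.** Take the eligible number as Bin(30, 0.95); independence between patients is an assumption. The mean is 30 × 0.95 = 28.5. P(26) = 4.5%, P(27) = 12.7%, P(28) = 25.9%, P(29) = 33.9%, P(30) = 21.5%, and P(25 or fewer) = 1.6%. So P(29 or 30) = 55%, and 29 is the most likely number.

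**4. Average type I error with 13 applied to all eligible.** Weighting step 2 by step 3: 0.0451 × 0.0251 + 0.1270 × 0.0349 + 0.2586 × 0.0469 + 0.3389 × 0.0609 + 0.2146 × 0.0770 = 0.0549. The small term for 25 or fewer brings it to 0.0551, or 5.5%. By assumed ineligibility:

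| ineligible | 0% | 2% | 5% | 6% | 7% | 10% |
|---|---|---|---|---|---|---|
| average type I error | 7.7% | 6.8% | 5.5% | 5.1% | 4.8% | 3.8% |

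**5. How often the verdict is in doubt.** Cut-offs 13 and 14 differ only when stage 1 is passed and exactly 13 are controlled. Under p = 0.30 that has probability 3.3% at n = 29 and 3.9% at n = 30; under p = 0.57, 5.6% and 4.1%. Weighted by step 3:
- p = 0.30: 0.339 × 0.033 + 0.215 × 0.039 = 1.9%
- p = 0.57: 0.339 × 0.056 + 0.215 × 0.041 = 2.8%

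**6. Cross-check.** The exact (Clopper-Pearson) one-sided 95% lower bound, as a single-stage figure that ignores the futility look, is 30.1% for 13/28, 28.9% for 13/29 and 27.9% for 13/30. Thirteen controlled therefore excludes the 30% null at 28 but not at 29 or 30.

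**The case against.** The strongest reply is that the final rule carries its own number. On that reading the decision is made on 28 patients, the two extra inclusions are a reserve, and section 13.4.1 only says on whom the rate and its interval are reported. Sections 13.2 and 13.4.1 are then compatible and the error is 4.7%. The reading is reasonable, but the text does not state it. Section 13.4.1 gives the primary analysis to all eligible patients, and no section says which 28 would count.

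It is also true that the protocol never applies 13 to 29 or 30 patients. The 6.1% and 7.7% are what follows if the only available threshold is carried over.

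Adjusting cut-offs for the attained sample size is often left to the SAP, which is not shown. That would answer a missing detail. Here the protocol itself pairs a rule for one number with a population of another.

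Three smaller points stand:
- Section 3 may use the word eligible loosely, so it is weak evidence of an intended analysis set of 30; it still needs aligning with 13.2.
- The bound comparison uses a one-sided limit to match the one-sided test. Section 13.4.1 plans a 95% interval without stating sidedness, and the two-sided exact lower limit for 13/28 is 27.5%, already below 30%.
- The practical effect is small for a single-arm proof-of-concept trial.

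**Conclusion.** The concern holds. The two-stage design is sound at exactly 28 patients and its arithmetic is correct. The fault is that the only success rule does not match the primary population, which at the plan's own ineligibility rate is more likely than not to exceed 28.

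If 13 is kept throughout, the stated one-sided 5% is exceeded at 29 and 30, by 1.1 and 2.7 percentage points. Averaged over the eligible number, the excess is about half a point at 5% ineligible and disappears between 6% and 7%. These figures assume exactly 14 patients at stage 1; the averages also assume independent ineligibility. The point should be fixed, but it does not undermine the design.

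**What to change.** **Preferred.** State in sections 13.2 and 13.4.1 that stage 1 uses the first 14 eligible patients, and the formal test the first 28, in order of inclusion. Report the all-eligible and ITT control rates as estimates with confidence intervals. If only 26 or 27 are eligible, keep 13.

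**Alternative.** List the cut-off by number analysed: 13 for 26, 27 or 28, and 14 for 29 or 30.

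Either version should also say what happens at 25 or fewer, a 1.6% chance under the binomial above. At 25, a cut-off of 12 gives type I error 4.3% and power 86.1%, while 13 gives power 75.9%.

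In both cases, align the target in section 3 with the 30 included in section 13.2.

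**Cost.** Wording in sections 3, 13.2 and 13.4.1, and no extra patients. Averages at 5% ineligible, with 13 kept whenever fewer than 28 are eligible:

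| rule | average type I error | average power |
|---|---|---|
| 13 on all eligible | 5.5% | 90.3% |
| first 28 eligible | 4.4% | 88.5% |
| cut-off by number | 3.6% | 87.5% |

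The lost power is the price of holding alpha. The cut-off by number is weakest above 28 at n = 29, the most likely number (86.4%). With only 26 eligible, power is 81.7% under either fix, as it is with 13 now.

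A separate editorial correction in section 13.2 is to relabel the 90% given as beta as power (beta is 10%). The design is unaffected.

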13.3 Analyzed Populations

Subjects will be included according to the Intent-to-Treat (ITT) analysis.

The safety population will comprise all patients included who receive at least one dose of treatment.

The population of patients eligible will consist of patients ITT having no major deviation judged on the criteria of inclusion and non-inclusion.

The protocol deviations will be reviewed by the principal investigators and classified minor or major deviations, and listed.

13.4 Efficacy Analyses

13.4.1 Primary endpoint analysis

Analysis of the primary efficacy endpoint will be conducted on all eligible patients, based on the disease control rate after 8 weeks of treatment. Analysis of the primary efficacy endpoint will be also conducted on all patients (ITT analysis) as sensitivity analysis.

It will be presented associated with its 95% confidence interval. Patients for whom the answer cannot be evaluated will be considered as treatment failures.

13.4.2 Secondary endpoints

- Progression-free Survival (PFS) and Overall Survival (OS)

PFS is defined as the time between the date of inclusion and the first date of documented progression or death due to any cause, whichever occurs first. Subjects who die without a reported progression will be considered to have progressed on the date of their death. Subjects who did not progress or die will be censored on the date of their last evaluable tumor assessment.

The duration of overall survival is defined as the time elapsed between the date of inclusion and death. Subjects who did not die will be censored on the last date a subject was known to be alive.

The median survival, 95% confidence intervals and an estimation of progression-free survival (PFS) and overall survival according to the Kaplan-Meier Method will be calculated using standard methods

This analysis will be performed on all eligible patients.

PFS and OS will be also conducted on all patients (ITT analysis) as a sensitivity analysis.

- Tolerance

The toxicity analysis will be performed on the safety population.

13.5 Data Monitoring Committee

A Data Monitoring Committee (DMC) will be utilized to provide general oversight and safety considerations for this study. The DMC will provide advice to the Sponsor regarding actions the committee deems necessary for the continuing protection of subjects enrolled in this study. The DMC will be charged with assessing such actions in light of an acceptable risk/benefit profile for nivolumab. The DMC will act in an advisory capacity to IFCT and will monitor subject safety data for the study.

The DMC will be advisory to the clinical study leadership team. The clinical study leadership will have responsibility for overall conduct of the study including managing the communication of study data.

The Intergroup will be responsible for promptly reviewing the DMC recommendations, for providing guidance regarding the continuation or termination of the study, and for determining whether amendments to the protocol or changes to the study conduct are required.

A safety run will be done after the first 5 patients then every 10 patients (8 weeks follow up) and will be reviewed by the DMC in attempt to detect unexpected immunovirologic side effects, ie increase in HIV viral load, decrease of CD4 cell count or unexpected high frequency of IRIS.

Details of the DMC responsibilities and procedures will be specified in the DMC charter.

The DMC recommendations will be sent to ANSM for information.

14 CORRELATIVE BIOLOGICAL STUDIES (“BIO-CHIVA2”)

As for other trials previously conducted by the IFCT, several biological specimens will be centrally collected for correlative biological studies (BIO-CHIVA2). Two cores from archived or fresh paraffin embedded tissue specimens will be collected to perform IHC of PDL1 expression on tumoral and immune cells and other phenotyping biomarkers associated with immune check point inhibitors efficacy (CD8, HLADR, interferon gamma and foxp3).

Plasma will be also collected before treatment to evaluate the presence of circulating tumor DNA using a lung panel NGS approach. Presence, number of detected alterations and quantification of molecular alterations were correlated to the efficacy of nivolumab treatment.

These analyses will be performed by the GRC-04 Theranoscans laboratory of P&M Curie Paris 6 university (Pr [name], Pr [name], [name], [name]).

Otherwise, the HLA class I restriction of CD8 T cell plays an important role in the antiviral response in term of both repertoire and avidity of the cellular response (Lissina AIDS. 2014 Feb 20;28(4):477-86, Appay, Curr Opin HIV AIDS. 2011;6:157). But the efficacy of immune checkpoint inhibitors is based on the activation of the response of cytotoxic T cell. This response could be modulated by the HLA class I restriction. The modulation by immune checkpoint inhibitors of CD4+ T cells antitumor function, restricted to HLA class II, has also been described (Pardoll Nature Reviews Cancer 2012 ; 12, 252 ; Kwek, Cancer Immunol Res. 2015;3:1008). A HLA class I and II typing by standard technique (PCR-SSO) with a 2-digit resolution will be done in the biological study BIO-CHIVA-2 for all the patient and,

even more so, for patients experiencing immune related adverse events. This technique could be complemented by a technique with 4-digit alleles resolution.

Furthermore, all genes which have a major interest in the response to immune check point inhibitor or in the occurrence of an event will be sequenced after the registration of a significant number of patients. For that purpose, a dried cell pellet of 5 to 10 millions of PMBC will be stored for the genetic study of relationships between cancer and HIV infection.

14.1 Protocol for Immunology and Virology (Pitié Salpêtrière);

Samples for cell bank, plasma and serum analysis will be made by a 68 mL blood sample before first nivolumab infusion, at cycle 2, 3, 9, 15, 27, 51, at the end of treatment , and in the case of immune adverse effect. The following tubes will be collected and sent to the centralized laboratory within 24h:

- 6 acid Citrate Dextrose tubes of 9 mL
- 2 EDTA tubes of 7 mL

The plasma bank will measure the concentration of anti PD1 / PDL-1 and optionally the anti-antibody levels, and the residual HIV replication. The plasma dosage will also measure cytokines / chemokines and other inflammation markers based on scientific knowledge on the subject. The cell bank will: 1° / assess the size of the HIV reservoir (cell-associated DNA), 2° / assess the anti-HIV immune response (quantitative and qualitative study of antiviral T cells: count, polyfonctionality, expression of immune checkpoints ...), 3° / assess the state of differentiation / activation of T cells expressing immune checkpoints, 4° / evaluate the immune responses against the other virus (EBV, CMV, hepatitis B and C, HHV-8) if co-infected, and 5° / finally assess the anti-neoepitope CTL directed against tumor neoantigens. Finally, paraffin embedded tumor and peritumoral biopsies will be punched in centers in order to sample tumoral and healthy tissue; those punches will be rerouted to the immunology laboratory (Pitié Salpêtrière) in order to perform RNAseq studies, then identification of tumoral neo-epitopes by sequence alignment, HLA typing, and finally neoepitope prediction. If punch sample is not available, FFPE tumor slides will be rerouted to the Pitie Salpetrire hospital: 20m thickness or 4x10m thickness, for tumoral whole exome sequencing and definition of neoepitopes.

15 ADMINISTRATIVE SECTION

15.1 Sponsor obligations

Before the trial

The sponsor will:

- Ensure regulatory requirements are met before the trial is implemented
- Ensure that all administrative procedures are in place for each department in the associated establishments
- Provide centres with the complete protocol and its appendices, the adverse event report form, CPP (Independent ethics committee) permission, statement of insurance and authorization from the French health authority (ANSM).

The sponsor and their representatives will:

- Provide centres with the instructions and documents needed to conduct the trial properly (protocol, data collection form and investigator file)
- Organise an orientation session to train study investigators and coordinators (during this session, all protocol sections will be reviewed and how to fill out case report forms and study procedures will be explained)

During the trial

The sponsor and their representatives will:

- Regularly visit the investigating centres
- Be available at all times for consultation and remain in contact with the personnel of the investigating centre by email, telephone and/or fax
- Examine and evaluate the data in the case report form and look for possible errors in data collection

In cooperation with the principal investigator, the sponsor will provide all of the investigators involved with the study with any new information that may interfere with conducting the trial.

In terms of the trial

It is the sponsor's responsibility to make sure that the procedures are completed at the end of the trial.

